2.3.2. Protocol Deviations

Protocol deviations are defined as instances where the protocol requirements are not followed in such a manner whereby data is unusable or unavailable. Protocol deviations are less serious in nature as long as they do not have an effect on the rights, safety or welfare of the study subject.

STATISTICAL ANALYSIS PLAN

Protocol deviations include, but are not limited to:

- Examinations/test/assessment not performed within the allowed follow-up window
- Required data not obtained

The study site should report the protocol deviation on the applicable CRF page.

2.4. Statistical Analyses

2.4.1. Patient Disposition and Follow-up

The number and percentage of patients included in each population and the reasons of non-inclusion in each subsequent population will be presented on the ITT population. The distribution of populations by site will be presented as well.

The number and percentage of patients present at each visit will be presented on the ITT and the As-treated population with the study exit reasons.

The average time of patient follow-up will be given on the ITT and on the As-treated population.

2.4.2. Baseline (Screening) Patient Characteristics

Descriptive statistical data will be used to draw up a recapitulation of the characteristics of the patients at the time of Enrollment/Screening visit.

The following data will be presented on the ITT and the As-treated populations:

- Demographics and Physical Exam: Age at Enrollment, Height (cm), Weight (kg), BMI (kg/m²), Temperature (°C), Blood pressure (Systolic and Diastolic in mmHg), Heart rate (bpm), Pregnancy test performed (Yes/No), the result if Yes and the reason if No or Not applicable, Specific abdominal examination performed (Yes/No), Presence of nodules or bumps if Yes (Yes/No) and How many nodules or bumps if Yes, Specific gynecologic examination performed (Yes/No), Presence of nodules or bumps in the cul-de-sac if Yes (Yes/No) and How many nodules or bumps in the cul-de-sac if Yes, Ovarian cancer stage, ECOG performance status.
- Medical History: Neurological, Respiratory, Smoker or past smoker (Yes/No), if Yes Current/Past and if Yes the number of years smoking, Arrhythmia, Symptomatic congestive heart failure, Unstable angina pectoris, Myocardial infarction, Ischemic heart disease, Pulmonary embolism, Deep vein thrombosis, Genitourinary, Allergy/Immunologic, Psychiatric, Current active infection and At least one other medical history.
- Specific Cancer History: Prior treatment with abdominal and/or pelvic radiotherapy, Presence of central nervous system or cerebral metastases, Recurrent ovarian cancer, History of other cancer, Hypersensitivity to carboplatin or paclitaxel, Current treatment using other antineoplastic agents, Type of debulking surgery planned, Three or four rounds of chemotherapy given prior to surgery if interval (Yes/No) and specification of the number if Yes.
- Peritoneal Carcinomatosis Index (PCI): Peritoneal Carcinomatosis Index (PCI) performed (Yes/No), PCI score if Yes, Detail of PCI scores (Region, Maximum lesion size (cm) and Lesion size score).
- Biomarker CA-125: Biomarker CA-125 (test performed Yes/No) and the Biomarker CA-125 result (U/mL). The analysis of the Biomarker CA-125 will be performed on primary debulking surgery (PDS) patients, interval debulking surgery (IDS) patients and overall.
- CT Scan: Abdominal CT Scan obtained, Pelvic CT Scan obtained, Chest CT Scan obtained, Lesions Sites, Lesions location, Lesions measurable (Yes/No), Lesions Measurements (mm) if measurable.
- Medications: Patient receiving any concomitant medication (Yes/No).

STATISTICAL ANALYSIS PLAN

2.4.3. Procedure (D0) Patients characteristics

Descriptive statistical data will be used to draw up a recapitulation of the intervention details at the time of the operation.

The following data will be presented on the ITT and the As-Treated populations:

- Physical exam: Weight (kg), BMI (kg/m²), Temperature (°C), Blood pressure (Systolic and Diastolic in mmHg), Heart rate (bpm), Specific abdominal examination performed (Yes/No), Presence of nodules or bumps if Yes (Yes/No) and How many nodules or bumps if Yes, Specific gynecologic examination performed (Yes/No), Presence of nodules or bumps in the cul-de-sac if Yes (Yes/No) and How many nodules or bumps in the cul-de-sac if Yes, Pre-operative serum albumin (g/dL) and Pre-operative hemoglobin (g/dL).
- Procedural Information: Type of debulking surgery, Debulking surgery duration (HH:MM), Pre-debulking PCI performed (Yes/No), PCI score if Yes, Detail of PCI scores (Region, Maximum lesion size (cm) and Lesion size score), Post-debulking PCI performed (Yes/No), PCI score if Yes, Detail of PCI scores (Region, Maximum lesion size (cm) and Lesion size score), Extensive upper abdominal surgical procedures (Diaphragm peritonectomy, Splenectomy, Full-thickness diaphragm resection, Partial hepatectomy, Distal pancreatectomy, Cholecystectomy), Other surgical procedures (Unilateral/bilateral salpingo-oophorectomy, Hysterectomy, Omentectomy, Large bowel resection, Pelvic lymph node dissection, Para-aortic lymph node dissection, Appendectomy, Thoracoscopy, Small bowel resection, Ileostomy, Colostomy, Inguinal lymph node dissection, Other), total number of extensive procedures, total number of other surgical procedures, total number of extended procedures (Patankar definition).Residual Tumor Characterization: Residual tumor observed after debulking (Yes/No), Can the patient be treated with M-Trap and the reasons if No, Device implant procedure duration (HH:MM), Suture used diameter (USP designation).
- Device: Successful implantation (Yes/No), The reason if No, Localization of implant.
- Post-Procedure Ultrasound: Abdominal ultrasound obtained (Yes/No), Reasons if No.
- Device deficiencies: Device malfunction occur during the procedure (Yes/No), If Yes Device deficiency description.

The analysis of the PCI and the residual tumor observed after debulking will be performed on PDS patients, IDS patients and overall.

2.4.4. Follow-up Patients characteristics

Descriptive statistical data will be used to draw up a recapitulation of patients' follow-up visit characteristics.

The following data will be presented on the as-treated population at 1Month, 3Months, 6Months, 9Months, 12Months, 15Months and 18Months follow-up visits:

- Physical exam: Weight (kg), BMI (kg/m²), Temperature (°C), Blood pressure (Systolic and Diastolic in mmHg), Heart rate (bpm), Specific abdominal examination performed (Yes/No), Presence of nodules or bumps if Yes (Yes/No) and How many nodules or bumps if Yes, Specific gynecologic examination performed (Yes/No), Presence of nodules or bumps in the cul-de-sac if Yes (Yes/No) and How many nodules or bumps in the cul-de-sac if Yes.
- Chemotherapy: Is chemotherapy complete (Yes/No), Number of IDS patients complete chemotherapy by the 3-month visit, Number of PDS patients complete chemotherapy by the 6-month visit, Number of cycles received since last visit, Is this visit the first one since the completion of chemotherapy (Yes/No), The reasons if chemotherapy is not completed
- Biomarker CA-125: CA-125 test performed (Yes/No), CA-125 results (U/mL), Disease progression as defined by CA-125 criteria (Yes/No).
- CT Scan: Abdominal CT Scan obtained, Pelvic CT Scan obtained, Chest CT Scan obtained, Target lesions site, Target Lesion location, Target Lesion Measurement (mm), New Target lesion, Evaluation of Target Lesions after chemotherapy completion, Non-Target Lesion Sites, Non-Target

STATISTICAL ANALYSIS PLAN

lesion location, Measurement of Non-Target lesion if measurable (mm), New Non-Target lesion, Evaluation of Non-Target Lesions after chemotherapy completion, Objective Subject Response.

CT Scan is not performed at 1Month visit.

- Device(s) Removal: Device(s) removal planned during this visit (Yes/No)
- Ultrasound: Abdominal Ultrasound obtained (Yes/No), The reason specification if No
- Medications: Medication(s) change since last visit (Yes/No)
- Adverse Event: New adverse events occur since last visit (Yes/No)

2.4.5. Primary Analysis

Primary analysis of safety will be performed on the ITT population and the As-Treated populations.

The primary safety endpoint is freedom from device and procedure-related major adverse events through 6-months post-implantation, including shock, cardiac arrest, myocardial infarction, pulmonary embolism, prolonged intubation, unplanned reintubation, or adverse events leading to removal of the device, including infection, seroma formation, mesh migration, bowel obstruction, adhesions, and local cancer progression through the abdominal wall at M-Trap suture sites.

The primary safety endpoint will be analyzed using a unilateral one sample test for binomial proportion at the 5% level. In addition, the exact bilateral 95% confidence interval will also be given. The statistical test for the primary safety endpoint is given by:

- H0: M-Trap freedom MAE incidence \leq 90% - Non-inferiority margin (25%)
- Versus
- HA: M-Trap freedom MAE incidence $>$ 90% - Non-inferiority margin (25%)

A modified primary analysis will also be performed that uses a freedom from MAE incidence rate that is adjusted for the surgical complexity of the study population, as compared to the Patankar study population, which is the basis of the statistical rationale for this study (repeated in the table below). The total number of extended procedures will be split in four classes: 0, 1, 2, 3 and more.

Procedures	0	1	2	3 or more	AVG
Total patients	1352	1214	254	50	2870
Severe complications, n	51	92	44	9	196
Severe complications, %	3.8%	7.6%	17.3%	18.0%	6.8%

A further modified primary analysis will also be performed that only includes procedure-related events through 30 days, as this is the comparable population to the Patankar study population, which is the basis of the statistical rationale for this study.

Primary analysis of performance will be performed on the As-Treated population and by device location. This analysis will be also performed using these 3 following sub-populations: (1) platinum resistant, recurrent patients; (2) platinum sensitive, recurrent patients; (3) non-recurrent patients (see definition in part 2.5).

The primary performance endpoint is histopathologic evidence of tumor cell capture (see 2.5). Histopathology will be performed after device explant.

The primary performance endpoint will be assessed with exact one-sided 90% confidence intervals.

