Published literature supports major adverse event rates of 10% for advanced ovarian cancer patients undergoing cytoreductive surgery. In a comprehensive analysis of 30-day post-operative complications in 2,870 patients undergoing surgery for ovarian cancer between 2005-2012, Patankar et. al. demonstrated a rate of severe complications of 6.8% and a rate of any complications of 11.9%, depending on the number of procedures performed during the cytoreductive surgery, as shown in **Table A** below. Any complication was defined as a composite measure if the patient was noted to have any of the following postoperative complications: pneumonia, acute renal failure, urinary tract infection, cerebrovascular accident, coma, sepsis, shock, cardiac arrest, myocardial infarction, pulmonary embolism, deep venous thrombosis, prolonged mechanical ventilation, unplanned re-intubation, or progressive renal insufficiency. Severe complications were analyzed based on Clavian class IV complications and included shock, cardiac arrest, myocardial infarction, pulmonary embolism, prolonged intubation or unplanned reintubation.

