#### **7.1.1. Anticipated or Potential Adverse Events**

The list below provides anticipated or potential adverse events that may occur during the study.

Adverse events that may be associated with a general surgical procedure are:

- Allergic reactions or hypersensitivity to medication, including anesthesia
- Anesthesia complications
- Bleeding
- Death
- Deep vein thrombosis
- Delayed or impaired wound healing
- Infection

Adverse events that may be associated with the surgical debulking procedure are: 

- Abdominal collection requiring drainage
- Abscess
- Acute cardiopulmonary failure
- Acute renal failure
- Anastomotic leak or failure
- Anemia
- Bowel / intestinal obstruction
- Cardiac failure / cardiac arrest / myocardial infarction
- Cardiac dysrhythmia
- Cerebrovascular accident
- Coma
- Death
- Deep vein thrombosis
- Diarrhea
- Fever
- Fistula
- Hematoma
- Hemoperitoneum
- Hemorrhage / bleeding
- Hypotension

- Ileus
- Infection
- Nausea
- Pain
- Pancreatitis
- Pancreatic leak
- Perforation
- Pericardial effusion
- Peritonitis
- Pleural effusion
- Pleuresia
- Pneumonia
- Pneumonitis
- Pneumothorax requiring placement of a chest tube
- Prolonged mechanical ventilation
- Prolonged or unplanned reintubation
- Pulmonary embolism
- Renal insufficiency or failure
- Reoperation
- Respiratory complication
- Respiratory distress syndrome
- Sepsis
- Seroma formation
- Shock
- Surgical site infection
- Thromboembolism
- Trauma
- Urethral obstruction
- Vomiting
- Wound dehiscence

Additional adverse events that may be associated with the device removal and cytology/biopsy laparoscopy procedure are:

- Adhesions
- Anesthesia-related complications
- Bruising
- Conversion to laparotomy
- Cyst rupture
- Hematoma
- Incisional hernia
- Injury to blood vessels of the abdominal wall or those of the lower abdomen and pelvic sidewall
- Peritonitis
- Port-site metastases
- Tumor cell peritoneal dissemination (seeding)
- Urinary tract or bowel injury
- Wound infection

Adverse events that may be associated specifically with the M-Trap device are:

- Adhesions
- Bleeding
- Fistula
- Hematoma
- Infection including abscess formation
- Inflammation
- Local cancer progression through the abdominal wall at M-Trap suture sites
- Mesh migration
- Obstruction
- Organ or bowel injury resulting from device removal procedure
- Pain
- Perforation
- Seroma formation

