## 8.3. Causality Relationship

The investigator will assess the causality of all adverse events in relation to the research, i.e., the relationship between the AE / SAE and the investigational treatment or any other study-related procedures.

Each event will be classified according to five different levels of causality:

**Not related:** relationship to the device or procedures can be excluded when:

- the event is not a known side effect of the product category the device belongs to or of similar devices and procedures;
- the event has no temporal relationship with the use of the investigational device or the procedures;
- the serious event does not follow a known response pattern to the medical device (if the response pattern is previously known) and is biologically implausible;
- the discontinuation of medical device application or the reduction of the level of activation/exposure - when clinically feasible – and reintroduction of its use (or increase of the level of activation/exposure), do not impact on the serious event;
- the event involves a body-site or an organ not expected to be affected by the device or procedure;
- the serious event can be attributed to another cause (e.g. an underlying or concurrent illness/ clinical condition, an effect of another device, drug, treatment or other risk factors);
- harms to the subject are not clearly due to use error;
- In order to establish the non-relatedness, not all the criteria listed above might be met at the same time, depending on the type of device/procedures and the serious event.

**Unlikely:** the relationship with the use of the device seems not relevant and/or the event can be reasonably explained by another cause, but additional information may be obtained.

**Possible:** the relationship with the use of the investigational device is weak but cannot be ruled out completely. Alternative causes are also possible (e.g. an underlying or concurrent illness/ clinical condition or/and an effect of another device, drug or treatment). Cases where relatedness cannot be assessed or no information has been obtained should also be classified as possible.

**Probable:** the relationship with the use of the investigational device seems relevant and/or the event cannot reasonably be explained by another cause, but additional information may be obtained.

**Causal relationship:** the serious event is associated with the investigational device or with procedures beyond reasonable doubt when:

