Add 1 to the score if Large bowel resection is ticked (colectomy, rectosigmoid resection).

Add 1 to the score if Diaphragm peritonectomy or Full-thickness diaphragm resection (diaphragm resection) is ticked.

Add 1 to the score if Partial hepatectomy (hepatic resection) is ticked.

- Derived criterion “freedom of device- and procedure-related major adverse events through 6 months post-implantation, including shock, cardiac arrest, myocardial infarction, pulmonary embolism, prolonged intubation, unplanned reintubation, or adverse events leading to removal of the device, including infection, seroma formation, mesh migration, bowel obstruction, adhesions, and local cancer progression through the abdominal wall at M-Trap suture sites” which is the primary endpoint will be calculated as follows:

If a MAE occurred in a patient within 6 months \pm 2W post implantation and “Does this event meet the definition of a major adverse event for the primary endpoint?” = “Yes” then “freedom of device- and procedure-related major adverse events through 6-months post-implantation” = “No” else “freedom of device- and procedure-related major adverse events through 6-months post-implantation” = “Yes”.

- Derived criterion “recurrent patients” will be defined as patients with device removal reason “Disease progression as defined by objective RECIST 1.1 and CA-125 criteria” or device removal reason “other” that indicates recurrence. Derived criteria “non-recurrent patients” are the remaining patients. CRO will send to MTrap an excel file with the list of all other reason of device removal to identify the reason that indicates “recurrence”.
- Derived criterion “time to recurrence” will equal to the date of the follow-up visit when “Device removal planned for this visit” is yes minus the procedure date.
- Derived criterion “platinum resistant, recurrent patients” will be defined as “recurrent patients” where the difference between the date of the follow-up visit when “Device removal planned for this visit” is yes and the date of the most recent chemotherapy medication treatment is less than or equal to 180 days.
- CRO will send to MTrap an excel file with the list of the concomitant medication to identify the chemotherapy medication treatment. Derived criterion “platinum sensitive, recurrent patients” will be defined as “recurrent patients” that are not “platinum resistant, recurrent patients”.

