- Histopathologic evidence of tumor cell capture is “Yes” if Tumor cell infiltration for at least one device is >0 in a patient. Otherwise, Histopathological evidence of tumor cell capture is “No”.
- An AE will be considered as an SAE if “Serious Adverse event” = “Yes”.
- An AE will be considered “Unanticipated” if “Anticipated adverse event” = “No”.
- An AE will be considered as device related if “Relationship to device(s)” is “possible”, “probable” or “definite”.
- An AE will be considered as procedure related if “Relationship to procedure” is “possible”, “probable” or “definite”.
- At least one other medical history will be calculated as follows:

If at least one variable of other medical history is equal to “Yes” then “At least one other medical history” = “Yes”,

If no variable of other medical history is equal to “Yes” then:

- If all variables of other medical history are equal to “No” then “At least one other medical history” = “No”,
- If at least one variable of other medical history is equal to “Missing” then “At least one other medical history” = “Missing”,

If all variables of other medical history are equal to “Missing” then “At least one other medical history” = “Missing”.

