Table 55: Non-inferiority on Freedom of device and procedure related MAE through 6-months on AT population (Type 5)

Table 56: Freedom of device and procedure related MAE through 6-months on AT population using MAE expected incidence adjusted for the study population number of extended procedures (Patankar definition) (Type 8)

Table 57: Freedom of device and procedure related MAE through 30 days on AT population using MAE expected incidence adjusted for the study population number of extended procedures (Patankar definition) (Type 5)

Primary Performance analysis

Table 58: Histological evidence of tumor cell capture in at least one M-Trap device after device explant on AT population by device location (Type 2)

Table 59: Histological evidence of tumor cell capture in at least one M-Trap device after device explant on AT population with sub-analysis of histological evidence of tumor cell capture by device location and recurrence status (Type 2)

Secondary Analysis

Secondary Safety analysis

Table 60: AEs on ITT population (Type 6)

Table 61: AEs on AT population (Type 6)

Table 62: SAEs on ITT population (Type 6)

	STATISTICAL ANALYSIS PLAN	MTRAP_SAP_v2.0_FINAL redacted.docx
		MTRAP Page 19/20

Table 63: SAEs on AT population (Type 6)
 Table 64: M-trap device related AEs on ITT population (Type 6)
 Table 65: M-trap device related AEs on AT population (Type 6)
 Table 66: M-trap device related SAEs on ITT population (Type 6)
 Table 67: M-trap device related SAEs on AT population (Type 6)
 Table 68: Unanticipated M-trap device related AEs on ITT population (Type 6)
 Table 69: Unanticipated M-trap device related AEs on AT population (Type 6)
 Table 70: Unanticipated M-trap device related SAEs on ITT population (Type 6)
 Table 71: Unanticipated M-trap device related SAEs on AT population (Type 6)
 Table 72: M-trap procedure related AEs on ITT population (Type 6)
 Table 73: M-trap procedure related AEs on AT population (Type 6)
 Table 74: M-trap procedure related SAEs on ITT population (Type 6)
 Table 75: M-trap procedure related SAEs on AT population (Type 6)
 Table 76: Device deficiencies on ITT population (Type 5)
 Table 77: Device deficiencies on AT population (Type 5)
 Table 78: Mortality rate on ITT population (Type 5)
 Table 79: Mortality rate on AT population (Type 5)

Secondary performance analysis

Table 80: Disease focalization scores of I on AT population (Type 5)
 Table 81: Disease focalization scores of I or II on AT population (Type 5)

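### The 30-day safety analysis offered as comparable to the historical cohort counts only procedure-related events, Table 57 describes a different event set, and SAP 2.5 has no 30-day variable to settle which applies

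*SAP*

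**What the plan says.** - **SAP 2.4.5, text.** After the main 6-month test and a complexity-adjusted version of it, the SAP adds: "A further modified primary analysis will also be performed that only includes procedure-related events through 30 days, as this is the comparable population" to the cited surgical cohort. The section opens by placing primary safety analysis on both the ITT and the As-Treated (AT) populations.
- **Protocol 1.5, the cohort.** It covers 2,870 patients with 30-day post-operative complications and a severe-complication rate of 6.8%. Severe complications "included shock, cardiac arrest, myocardial infarction, pulmonary embolism, prolonged intubation or unplanned reintubation". Relatedness is not mentioned.
- **SAP 4.1, the output.** "Table 57: Freedom of device and procedure related MAE through 30 days on AT population using MAE expected incidence adjusted for the study population". The adjustment is for surgical complexity, measured by how many extended procedures each patient had.
- **SAP 2.5, the derivations.** There is one MAE-freedom variable. Its window is 6 months ± 2 weeks, and it is driven by the CRF question "Does this event meet the definition of a major adverse event for the primary endpoint". Separately, "An AE will be considered as procedure related if" its relationship to the procedure is recorded as possible, probable or definite.
- **Protocol 8.3, causality.** Grounds for *not related* include that "the serious event can be attributed to another cause (e.g. an underlying or concurrent illness/ clinical condition", or another drug or treatment. In the other direction, "Cases where relatedness cannot be assessed or no information has been obtained should also be classified as possible".
- **Protocol 7.1.1.** The events anticipated with debulking include "Cardiac failure / cardiac arrest / myocardial infarction", shock, pulmonary embolism, prolonged ventilation and reintubation.

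**The concern.** This is the only safety analysis whose time window matches the cohort's, and the SAP presents it as the like-for-like comparison. A matching window is not enough if the two sides count events differently. On the trial side, an early severe event counts only if an investigator in a non-blinded study judges it related to the procedure. On the cohort side, as the protocol describes it, the event simply had to occur.

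The text and the table also do not describe the same analysis. With no 30-day variable defined, the choice of event set, population and reference rate would fall to whoever programs the output. With so few patients, one event classified one way or the other is visible in the reported rate.

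**Working it through.** **1. The plan's own figures.** From Protocol Table A and the SAP 2.4.5 table, the severe rate is r = 196/2870 = 6.83%, the stated 6.8%. The main test also reproduces: with n = 20 and H0 at 90% − 25% = 65%, the exact rule is at least 17 of 20 event-free, giving one-sided alpha 0.044 and power 0.867 at 90%. Neither figure is in dispute.

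**2. The descriptions side by side.**

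| | Cohort (Protocol 1.5) | SAP 2.4.5 text | Table 57 | SAP 2.5 variable |
|---|---|---|---|---|
| Window | 30 days | 30 days | 30 days | 6 months ± 2 weeks |
| Attribution | none described | procedure-related | device- and procedure-related | through the primary-endpoint flag |
| Device-removal events | not listed | not stated | within the MAE definition | within the MAE definition |
| Population | surgical cohort | ITT and AT (section opening) | AT only | not stated |
| Reference rate | 6.8% overall | not stated for this analysis | complexity-adjusted | none |

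The trial columns differ on attribution and population, and only Table 57 states the adjusted reference. *Further modified* in the text may imply that reference but does not say so.

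**3. How much one event weighs.** Expected events at r are 20 × 0.0683 = 1.37, or 22 × 0.0683 = 1.50. One event moves the rate by 1/20 = 5.0 points, or 1/22 = 4.5 points.

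**4. Effect of the filter.** Let s be the share of severe 30-day events judged unrelated. The documents give no value. The range 0 to 25% is an assumption, and the low end is more likely for the reasons given under the objection. The measured rate is r(1 − s). The chance that at least one of 20 patients has an event removed is 1 − (1 − rs)^20.

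| s | Measured rate | Chance of at least one event removed | P(at least 17 of 20 event-free) |
|---|---|---|---|
| 0 | 6.83% | 0 | 0.956 |
| 0.10 | 6.15% | 0.128 | 0.969 |
| 0.25 | 5.12% | 0.291 | 0.983 |

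The last column borrows the main test's rule for illustration, because the SAP sets none for this analysis. A pass or fail reading would hardly move.

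**The case against.** The strongest reply is that the filter will remove almost nothing. *Possible* counts as related, unassessable cases default to *possible*, and the cohort's event types are anticipated complications of debulking. An investigator would rarely call such an event unrelated within 30 days of that operation. This stands, and it is why the gap is probably small. It does not close the gap: Protocol 8.3 still allows *not related* or *unlikely* where another cause can explain the event. Sponsor and DSMB review of all adverse events (Protocol 7.1.2) does not help, since nothing there says attribution may be changed.

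The reply also depends on what *procedure* means. Protocol 5.3.2 places the index procedure after debulking, and Tables 72-75 speak of M-Trap procedure-related events, whereas SAP 2.4.3 records debulking as procedural information. If only implantation is meant, the filter could remove more.

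A second reply is that Protocol 1.5 is a short summary. It is silent on attribution and introduces the event types with *included*, so the list may not be complete. This stands as a limit. A reader might infer that the cohort is known to be unfiltered; the documents support only that no filter is described.

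A reader might also infer that device-removal events, which the MAE definition includes and the cohort's list does not, would push the 30-day rate up materially or cancel the filter. Protocol 6.2.3 places removal after chemotherapy is completed, and the schedule's footnotes tie the final infusion to the 3- or 6-month visit. Removal within 30 days is therefore a remote route; mainly an early-onset event that led to later removal could enter.

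Finally, a programmer could combine the existing flag, relationship field and onset date, and the wording of Table 57 may simply be carried over from Tables 55 and 56. Both are plausible, but the SAP says neither.

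**Conclusion.** The point holds, at low weight. An analysis offered as comparable to the cohort applies an attribution filter that the cohort, as described, does not have. Text and table give different event sets and populations, and no derived variable decides between them. The mismatch between text and table and the missing derivation are internal to the SAP and stand whatever the cohort publication says. The filter point rests on the protocol's description of the cohort.

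The filter can only lower the trial's rate. Its size cannot be computed from the documents; the measured rate of 6.8% falling to 5.1% spans the assumed 0 to 25% and is not an estimate. The practical weight is that about 1.4 events are expected in 20 patients and each is worth 5 points.

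A reader might infer that the trial's safety conclusion is biased in the device's favour. The documents do not support that. This is a supportive analysis without a decision rule, and the main 6-month test against 65% and its sample size do not depend on it.

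**What to change.** 1. In the 30-day analysis, report the severe event types listed in Protocol 1.5 from day 0 to day 30, regardless of attribution and without device-removal events. Show the procedure-related count alongside.
2. Add that 30-day criterion to SAP 2.5, with its event types and day count.
3. Make SAP 2.4.5 and Table 57 name the same event set, the same population (ITT, AT or both) and the same reference rate.
4. State whether *procedure* covers debulking as well as implantation wherever procedure-relatedness is used.

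The cost is SAP wording, one derived variable and one extra column. No new data are needed: Protocol 8.4 already has every adverse event recorded with its description, onset date and relationship, whatever the causality. All-cause events are already tabulated in Tables 60-63, but without a 30-day window. The downside is possibly a few more counted events.
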